3.3.2.11 Corrected QTc Prolongation

The effect of orally administered cabozantinib 140 mg qd on QTc interval was evaluated in a placebo-controlled study in subjects with MTC. A mean increase in QTcF of 10-15 ms was observed after 4 weeks after initiating cabozantinib treatment. A concentration-QTc relationship could not be definitively established. Changes in cardiac wave form morphology or new rhythms were not observed. No cabozantinib-treated subjects in this study had a QTcF $> 500 \text{ ms}$.

Unless otherwise specified in certain protocols, only subjects with a baseline QTcF $\leq 500 \text{ msec}$ are eligible for cabozantinib research studies. Cabozantinib should be used with caution in subjects with QT prolongation risk, a history of QT interval prolongation, or who are taking antiarrhythmics or drugs

Proprietary Information of MD Anderson

known to prolong the QT interval. Concomitant treatment with strong CYP3A4 inhibitors, which may increase cabozantinib plasma concentrations, should be avoided.

If at any time on study there is an increase in QTcF to an absolute value > 500 ms or an increase of > 60 ms above baseline, two additional ECGs must be performed with intervals not less than 3 min apart within 30 min after the initial ECG.

If the average QTcF from the three ECGs is > 500 ms or increased by > 60 ms above baseline, the following actions must be taken:

- Withhold study treatment
- Immediately notify the MD Anderson IND Office
- Hospitalize symptomatic subjects (e.g., with palpitations, dizziness, syncope, orthostatic hypotension, a significant ventricular arrhythmia on ECG) for a thorough cardiology evaluation and management
- Consider cardiology consultation for asymptomatic subjects for evaluation and management
- Check electrolytes, especially magnesium, potassium and calcium; correct abnormalities as clinically indicated
- Check concomitant medications for any medication that may have contributed to QT prolongation, and if possible, discontinue these medications (<http://www.qtdrugs.org>)
- Repeat ECG triplices hourly until the average QTcF is ≤ 500 msec, or otherwise determined by consultation with a cardiologist or appropriate expert.

Subjects with QTc prolongation and symptoms must be monitored closely until the QTc elevation and symptoms have resolved. Study treatment may be restarted at a reduced dose level if all of the following conditions are met:

- Symptoms are determined to be unrelated to the QT interval prolongation
- The QTcF value > 500 ms or increase of > 60 ms above baseline is not confirmed according to protocol procedures
- Study treatment has been interrupted through a minimum of 1 week following the return of the QTcF to ≤ 500 msec or return to ≤ 60 ms above baseline.
- QT prolongation can be unequivocally associated with an event other than cabozantinib administration and is treatable/has been resolved
- Sponsor has reviewed all available information and has agreed to the continuation of study treatment

Following reinitiation of study treatment, ECGs must be repeated weekly for 2 weeks, then every 2 weeks for 1 month, then according to the protocol-defined time points.

All study treatment must be permanently discontinued if either of the following applies:

- Cardiac evaluation confirms that symptoms are the consequence of QT interval prolongation
- Recurrence of QTcF prolongation (confirmed by central ECG lab) after reinitiation of study treatment at a reduced dose

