cabozantinib dose to 80 mg a day if AUC for plasma cabozantinib was <50% of expected AUC provided AE levels are \leq grade 1. Further dose titration in these subjects to 60 mg, 40 mg and 20 mg will be done based on tolerability and adverse effects. The remaining study participants will have their samples analyzed after completing study enrollment.

•

Guidelines for the management of specific AEs are provided in Section 3.3.2.

Table 3-2: Dose Reductions of Cabozantinib

Assigned dose	First Dose Level Reduction	Second Dose Level Reduction
60-mg cabozantinib oral qd qd, once daily Cabozantinib should be discontinued if a qd dose of 20-mg cabozantinib (minimum dose) is not tolerated	40-mg cabozantinib oral qd	20-mg cabozantinib oral qd

Proprietary Information of MD Anderson

Table 3-3: Dose Modifications of Cabozantinib for Treatment-Related AEs

CTCAE v.4.0 Grade	Recommended Guidelines for Management ^a
Grade 1 AEs	Add supportive care as indicated. Continue cabozantinib treatment at the current dose level if AE is manageable and tolerable.
Grade 2 AEs which are tolerable and are easily managed	Continue cabozantinib treatment at the current dose level with supportive care.
Grade 2 AEs which are intolerable and cannot be adequately managed	
At the discretion of the investigator, cabozantinib should be dose reduced or interrupted.
 
Note: It is recommended that dose holds be as brief as possible.

Grade 3 AEs (except clinically non-relevant laboratory abnormalities)	
Cabozantinib should be interrupted unless the toxicity can be easily managed with a dose reduction and optimal medical care. Resume cabozantinib following recovery to Grade 1 (or baseline).
 
Note: It is recommended that dose holds be as brief as possible.

Grade 4 AEs (except clinically non-relevant laboratory abnormalities)	
Subjects should have cabozantinib interrupted immediately.
 
Discontinue cabozantinib unless the following criteria are met:
 
 • Subject is deriving clear clinical benefit as determined by the investigator and agreed by the MD Anderson IND Office • Toxicity can be managed with a dose reduction following recovery to Grade 1 (or baseline) and optimal medical care

AE, adverse event.

Note: The dose delay and modification criteria for specific medical conditions are provided in Section 3.3.2. For re-treatment criteria of study treatment after a dose hold see Section 3.3.1.1.

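### The QTc restart list does not say what counts as confirmation; if it is the triplicate average, no subject withheld on that average can meet the list

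*Combined protocol and SAP*

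**What the plan says.** Section 3.3.2.11 works in two steps. A single QTcF above 500 ms, or more than 60 ms over baseline, calls for two further ECGs, spaced by at least 3 minutes and done in the half hour after the first. The three are averaged, and the hold criterion opens: "If the average QTcF from the three ECGs is > 500 ms or increased by > 60 ms above baseline". If it is met, drug is withheld, the IND Office is notified at once, and triplicates are repeated hourly until the average is at or below 500 ms or an expert decides otherwise.

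The restart rule is: "Study treatment may be restarted at a reduced dose level if all of the following conditions are met". There are five conditions:

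1. Symptoms are judged unrelated to the prolongation.
2. "The QTcF value > 500 ms or increase of > 60 ms above baseline is not confirmed according to protocol procedures"
3. At least 1 week off drug has passed since QTcF came back within a limit.
4. "QT prolongation can be unequivocally associated with an event other than cabozantinib administration and is treatable/has been resolved"
5. The sponsor has reviewed the case and agreed.

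The section then provides for life after restart: "Following reinitiation of study treatment, ECGs must be repeated weekly for 2 weeks", with further ECGs to follow. Permanent discontinuation is required in two situations only. One is symptoms shown to be caused by QT prolongation. The other is: "Recurrence of QTcF prolongation (confirmed by central ECG lab) after reinitiation of study treatment at a reduced dose".

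The note under Table 3-3 points two ways. It says "The dose delay and modification criteria for specific medical conditions are provided in Section 3.3.2", and also "For re-treatment criteria of study treatment after a dose hold see Section 3.3.1.1".

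**The concern.** Condition 2 uses the same two thresholds as the hold criterion, but in the negative. A subject is held because the triplicate average exceeded a threshold, and may restart only if that excess is not confirmed. The text does not say what does the confirming. On the most direct reading the list shuts out everyone it was written for.

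What is at stake is a dosing decision for a rare patient: one whose QTcF rose for a clear reason other than the drug and has since returned. The section neither lists that patient for permanent discontinuation nor, on the direct reading, allows restart. The site must then guess. The trigger for a permanent stop after recurrence also depends on a laboratory that the protocol does not describe.

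**Working it through.** This is a check of logic. The plan states no figure to reproduce.

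**Inputs.** Hold (H): triplicate average over a threshold. Restart (R) = C1 and C2 and C3 and C4 and C5, because all five are required. Both come from Section 3.3.2.11. The central ECG lab appears once, in the recurrence rule. The ECG row of Table 5-1 and its footnote 8 cover routine monitoring and mention no central reading.

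**Three readings of confirmation in C2.**

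| Reading | C2 for a held subject | Consequence |
|---|---|---|
| A. Triplicate average | H means confirmed, so C2 is false | R is false for every held subject. C2 is true only when the average is below both thresholds, and this section does not hold drug for those subjects. |
| B. Central ECG lab | Can be true if the central reading disagrees with the site | Some held subjects pass C2. C4 still asks for the unequivocal cause of a prolongation that was not confirmed. A centrally confirmed, explained and resolved rise remains barred. |
| C. No longer shown when restart is considered | True once QTcF has returned | All five can be met, but C2 then largely repeats C3. |

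**Against the rest of the section.** C3 (QTcF has returned) and C4 (another cause) treat the prolongation as real. The ECGs after restart and the recurrence rule assume that restarts happen. Reading A makes all of these idle. Reading B leaves C2 and C4 in conflict. Only reading C makes the section work, and it is the least literal: C2 refers to the value that led to the hold. The hourly repeats also give an end point for the 500 ms threshold only, not for the 60 ms rise.

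**Size.** C2 changes the outcome only for a subject who triggers the hold and meets the other four conditions. Let r be the per-patient trigger rate and f the share of triggers meeting the other four. The documents give neither, so both are assumptions. With the maximum of 18 patients (Section 7.3):

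Expected number = 18 × r × f; chance of at least one = 1 − (1 − r × f)^18.

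| f | r = 0.1% | r = 1% | r = 2% |
|---|---|---|---|
| 1 (upper bound) | 0.018; 1.8% | 0.18; 16.5% | 0.36; 30.5% |
| 0.5 | 0.009; 0.9% | 0.09; 8.6% | 0.18; 16.5% |
| 0.1 | 0.0018; 0.18% | 0.018; 1.8% | 0.036; 3.5% |

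For example, with r = 1% and f = 1: 18 × 0.01 = 0.18, and 1 − 0.99^18 = 0.165.

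**The case against.** The strongest reply is that a workable reading exists. C2 is in the present tense and is checked at restart, and the section orders repeat triplicates. It could mean that prolongation no longer shows. This stands as a possible reading, so total exclusion is conditional. It does not remove the defect, because the text does not choose between the readings and the most direct one fails.

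A reader might infer that the protocol has no procedure for confirming a raised QTcF. The documents do not support that: number of ECGs, spacing, time window, averaging and thresholds are all given. What is missing is the statement that C2 refers to this procedure.

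A reader might also infer that Sections 3.3.2.11 and 3.3.1.1 direct opposite actions, since 3.3.1.1 lets a subject recovered from an unrelated toxicity resume at the same dose, without the 1-week wait or sponsor agreement. That is too strong. The Table 3-3 note sends specific conditions to Section 3.3.2, where the liver, hand-foot and proteinuria topics carry their own restart rules. Section 3.3.1.1 is permissive. Section 3.3.2 presumes attribution to study drug and makes the unrelated category very narrow. The IND Office also knows of every QTc hold. What remains is a small ambiguity over which section takes precedence.

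Scope is also arguable. The sentence just before the list concerns symptomatic subjects, and condition 1 presupposes symptoms. If asymptomatic subjects fall outside the list, the exclusion under reading A does not reach them, but the section then has no restart rule for them.

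Finally, central reading may be set out in a document outside the protocol. The text cannot rule this out, so the central-lab wording should not simply be struck.

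**Conclusion.** The restart list is inconsistent as written, and condition 2 needs correcting. That no withheld subject can restart follows only if confirmation means the triplicate average, which is the only procedure described. Under a central-lab reading the conflict with condition 4 remains.

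The impact is low. Section 3.3.2 calls prolonged QTc very rare. In the placebo-controlled study at 140 mg daily, no cabozantinib-treated subject exceeded 500 ms, and the starting dose here is 60 mg. That does not exclude rises above 60 ms, but it gives little support to the higher assumed rates. Condition 4 already bars any drug-caused rise. The literal reading fails safe, and a recurrence would still lead to a triplicate, a hold and notice to the IND Office; only the confirmation of the permanent stop is unclear. The counts above are upper bounds or illustrations resting on assumed r and f.

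This is a minor correction to a safety rule. It does not touch PFS4, the sample size or the stopping boundaries.

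**What to change.** - Reword condition 2 to require that QTcF above 500 ms, or more than 60 ms over baseline, is no longer present on repeat triplicate ECGs. Deleting it would also do, since condition 3 covers the return. Keep the other four conditions jointly required.
- If the clinical team does not want restart after a confirmed prolongation, state instead that a confirmed prolongation ends treatment.
- Add one sentence that the QTc list governs over Section 3.3.1.1.
- Let recurrence on the triplicate average trigger permanent discontinuation, unless a central ECG reading is actually in place; if it is, describe it.

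The cost is a short protocol amendment with IRB review. Clinical sign-off is needed, because allowing or forbidding restart after a confirmed, explained and resolved prolongation is a clinical decision. No new procedure, laboratory or patients are required.

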3.3.2.12 Hypophosphatemia

Hypophosphatemia has been reported during treatment with cabozantinib. Serum phosphorus should be monitored frequently while receiving cabozantinib. Other causes of hypophosphatemia should be ruled out and/or these causes treated in accordance to standard of care. Mild to moderate hypophosphatemia

Proprietary Information of MD Anderson

should be managed by oral replacement including food that are high in phosphate (diary items, meats, beans) and/or oral phosphate supplements in accordance to standard clinical practice guidelines.

Clinically relevant hypophosphatemia should be managed in accordance to the dose modification guidelines as outlined in Table 3-2 and Table 3-3 or as clinically indicated.

3.3.2.13 Thyroid Function Disorders

Changes in thyroid function tests (TFTs) and hypothyroidism have been reported with cabozantinib therapy and other tyrosine kinase inhibitors as a result of altered thyroid hormone regulation by mechanisms that seem to be specific for each agent. Currently available data are insufficient to determine the mechanism of TFT alterations and its clinical relevance. Routine monitoring of thyroid function and assessments for signs and symptoms associated with thyroid dysfunction is recommended before initiation and during treatment with cabozantinib. Management of thyroid dysfunction (eg, symptomatic hypothyroidism) should follow accepted clinical practice guidelines and dose modification guidelines as outlined in Table 3-2 and Table 3-3.

3.3.2.14 Hemorrhagic Events

Hemorrhagic events have been reported with cabozantinib. In order to mitigate risk of severe hemorrhage, subjects should be evaluated for potential bleeding risk factors before initiating cabozantinib treatment and monitored for bleeding events with serial complete blood counts and physical examination while on study. Risk factors for hemorrhagic events may include (but may not be limited to) the following:

- Tumor of the lung with cavitary lesions or tumor lesions which invades or encases major blood vessels. The anatomic location and characteristics of tumor as well as the medical history must be carefully reviewed in the selection of subjects for treatment with cabozantinib;
- Recent or concurrent radiation to the thoracic cavity;
- Active peptic ulcer disease, inflammatory GI diseases including Crohn's disease and ulcerative colitis;
- Underlying medical conditions which affect normal hemostasis (e.g., deficiencies in clotting factors and/or platelet function, or thrombocytopenia);
- Concomitant medication with anticoagulants or other drugs which affect normal hemostasis;
- History of clinically significant hemoptysis.

The risk of hemorrhage in cabozantinib-treated subjects with brain metastases has not been thoroughly analyzed. Though the incidence of CNS hemorrhage events in a study of subjects with GB was higher than observed in general population of subjects with cancer treated with cabozantinib, it is not clear how the risk of hemorrhage in GB translates to a risk of hemorrhage for subjects with brain metastases. Currently, brain metastases of carcinomas are not contraindications to the use of cabozantinib, but subjects with brain metastases should be monitored with a high index of suspicion if symptoms that could be due to a CNS hemorrhage occur.

Cabozantinib should be discontinued in subjects with serious and life-threatening bleeding events or recent hemoptysis (≥ 5 mL of red blood).

Proprietary Information of MD Anderson

3.3.2.15 GI Perforation/Fistula and Non-GI Fistula Formation

Gastrointestinal perforation/GI fistula: Prior to initiation of treatment with cabozantinib, subjects should be carefully evaluated for potential risk factors including (but not limited to) the following:

- Tumors invading GI or respiratory tracts
- Active peptic ulcer disease, inflammatory bowel disease (eg, ulcerative colitis, Crohn's disease), diverticulitis, cholecystitis or symptomatic cholangitis, or appendicitis
- History of abdominal fistula, GI perforation, bowel obstruction, or intra-abdominal abscess
- Ongoing visceral complications from prior radiation therapy
- Prior GI surgery (particularly when associated with delayed or incomplete healing)

Complete healing following abdominal surgery and/or resolution of intra-abdominal abscess must be confirmed prior to initiating treatment with cabozantinib.

After starting cabozantinib, subjects should be monitored for early signs of GI perforation such as abdominal pain, nausea, emesis, constipation, and fever especially if known risk factors for developing GI perforation or fistula are present.

Discontinue cabozantinib treatment in subjects who have been diagnosed with GI perforation/fistula.

Non-GI fistula formation: Complications from radiation therapy has been identified as a possible predisposing risk factor for fistula formation in subjects undergoing treatment with cabozantinib.

Subjects with any clinically relevant ongoing complications from prior radiation therapy (ie, radiation esophagitis or other inflammation of the viscera) should not be treated with cabozantinib.

Radiation therapy to the thoracic cavity (including mediastinum) should be avoided within 3 months of starting treatment with cabozantinib (excluding local radiation for bone metastases). Fistula should be ruled out as appropriate in cases of onset of severe mucositis or difficulty swallowing after start of therapy. Discontinue cabozantinib and initiate appropriate management in subjects who have been diagnosed with a non-GI fistula.

Discontinue cabozantinib treatment in subjects who have been diagnosed with non-GI fistula.

3.3.2.16 Osteonecrosis of the Jaw

Osteonecrosis of the jaw (ONJ) has been reported in subjects treated with cabozantinib. Additional risk factors for ONJ have been identified including the use of bisphosphonates and denosumab, chemotherapy, corticosteroids, local radiotherapy, and dental or orofacial surgery procedures.

Osteonecrosis of the jaw can manifest as jaw pain, osteomyelitis, osteitis, bone erosion, tooth or periodontal infection, toothache, gingival ulceration, or gingival erosion. Persistent pain or slow healing of the mouth or jaw after dental surgery may also be manifestations of ONJ.

Perform an oral examination prior to initiation of cabozantinib and periodically during cabozantinib therapy. Advise subjects regarding oral hygiene practice and to quickly report symptoms to investigator. Caution should be used in subjects receiving bisphosphonates.

Invasive dental procedures should be avoided. In cases where dental procedures are unavoidable, treatment with cabozantinib should be held for at least 4 weeks prior to the procedure and resumed after complete wound healing has occurred. Bone healing may often require a protracted time.

Proprietary Information of MD Anderson

3.3.2.17 Angioedema

Angioedema should be managed according to standard practice. The subject should be observed until symptoms resolve, with particular attention to maintaining an open airway.

3.3.2.18 Musculoskeletal and Connective Tissue Disorders

Cabozantinib appears to represent minimal risk of adverse musculoskeletal effects based on nonclinical GLP-compliant toxicology studies. The development of new or progressive, unexplained musculoskeletal symptoms such as pain or weakness should be assessed for underlying causes.

Rhabdomyolysis has been reported. Cabozantinib should be discontinued in subjects with serious and life-threatening rhabdomyolysis and interrupted if less severe forms occur when there are no other clear causes. Reinitiation of cabozantinib treatment must be discussed with and approved by the MD Anderson IND Office. Therapy of rhabdomyolysis should include supportive care and standard medical intervention.

3.3.2.19 Respiratory, Thoracic and Mediastinal Disorders

Dyspnea has been reported in clinical studies with cabozantinib. Symptoms should be managed according to locally accepted clinical practice including an assessment for underlying causes. Pulmonary embolism should be considered as possible causes for new onset dyspnea given the risk of thrombosis associated with inhibition of VEGF signaling. Furthermore, fistula formation (Section 03.3.2.15) and pneumonia have been reported in subjects treated with cabozantinib and should be considered as clinically indicated in subjects presenting with pulmonary symptoms.

3.4 Concomitant Medications and Therapies

3.4.1 Anticancer Therapy

Local intervention is discouraged unless medically unavoidable. Subjects receiving local intervention (e.g., palliative radiation) are allowed to continue to receive study treatment at the investigator's discretion.

